5.5.1 INITIAL UPDOSING / DOSE ESCALATION DAY

The starting dose of OIT in phase 2 will be individualised based on the outcome of the interim DBPCFC at 4-7 months, as shown in Table 7. The NOAEL (No Observed Adverse Event Level or highest dose not triggering symptoms) will be used as the tolerated dose. Mild transient symptoms (e.g. itchy mouth) to the reference dose (transient COFAR Grade 1 symptoms (Table 9) might be acceptable.

Tolerated dose (NOAEL) at 6 months DBPCFC	Initial dose for Phase 2 OIT		Max dose at Initial Escalation day	
	Step	CM Protein (mg)	Step	CM Protein (mg)
<0.5mg (i.e. 1 st dose reactor at FC)	1	0.04	6	2.5
0.5mg	3	0.2	6	2.5
3mg	4	0.4	7	6
10mg	6	2.5	8	15
30mg	9	30	n/a	n/a
100mg	10	60	n/a	n/a
300mg	10	60	n/a	n/a
1000mg or more	11	135	n/a	n/a

Table 7. Starting dose for OIT in Phase 2.

Participants starting phase 2 OIT at steps 1-6 will be offered to attend an escalation day visit at which up to 6 consecutive doses will be given by mouth at 20-30 minutes intervals under medical supervision on the Research Unit. As described in 5.3.2.1 (phase 1 escalation day), the supervising clinician will assess the participant to ensure suitability prior to dosing. If a given dose triggers symptoms that cause discomfort to the participant or deemed significant by the research team, no further doses will be administered on that day. Participants will be observed for at least one hour after dosing (2 hours if participant has previously experienced a delayed reaction). Participants will be instructed to have the last well-tolerated dose at home on a daily basis for a minimum of 10 days, until the next increase is performed.

At the discretion of the local investigator, participants commencing phase 2 OIT at step 9 or above do not need to attend for a separate escalation day:

- If the 2nd DBPCFC visit (at 6 months) is ACTIVE, then they can start the OIT dose the next day at home, unless there is doubt as to the dose tolerated at challenge (in which case a separate initiation visit should take place).
- If the 2nd DBPCFC visit is PLACEBO, then the initial OIT dose(s) can be given at the end of the 2 hour observation period of the challenge, where time permits.

Participants will then be asked to have their daily dose at home for a minimum of 10 days until the next increase is performed.

Prior to discharge home, patients will receive instructions including symptoms management and reporting as described in **5.3.2.1**.

5.5.2 UPDOSING (PHASE 2)

Updosing in Phase 2 will be performed in a similar manner to that in Phase 1 (section **5.3.2.1**). At each updosing visit, the dose will first be given under medical supervision, followed by observation for at least one hour (2 hours if participant has previously experienced a delayed reaction). Participants will then take that dose daily at home for a minimum of 10 days, until the next updosing visit. Once the target dose is reached (step 16), participants will continue this dose on a daily basis until the final assessment at 1 year has been completed.

5.5.3 DOSE PREPARATION FOR PHASE 2 OIT

Locally-sourced supermarket milk will be used for doses. Parents will receive written instructions on how to give doses at home.

The majority of participants are expected to start home dosing beyond step 9 i.e. with undiluted pasteurised milk available at supermarkets. For those few participants where diluted doses (steps 1 to 6) are needed, these will be provided with pre-labelled individual syringes containing the daily dose for the appropriate step. Families will be asked to store the syringes in their home freezer at -18°C in a plastic container. Each syringe will be used for a single dose, with the syringe taken out of the freezer 30 minutes prior to administration.

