5.3.1 TREATMENT ALLOCATION

[figure not shown]
OIT outcomes are affected by a range of variables, including age, allergen-specific IgE to CM, threshold and the presence of asthma. It is therefore essential to maintain balance between treatment groups with respect to these predictors. However, stratified randomisation using several variables is not effective in small trials. Minimisation is a valid alternative to ordinary randomisation, and has the advantage that there will be only minor differences between groups in baseline variables which are used in the allocation process.¹³ With minimisation, the treatment allocated to the next participant enrolled in the trial depends on the characteristics of those participants already enrolled, with an element of weighted randomisation – typically 80% chance – of each participant getting the allocation that minimises any imbalance.

Participants will therefore be allocated using an online minimisation/randomization tool, Minim, with a random element using a weighting probability of 0.8, stratified by centre. Baseline variables included in the minimisation will be:

- age (under 12yrs, 13+yrs)
- sex
- specific IgE to CM (<30 kU/l, \geq 30 kU/l)³
- eliciting dose at DBPCFC (\leq 44mg, 144-444mg, $>$ 444mg CM protein; these cut-offs are based on published population-based dose distributions in CM-allergic children)
- documented tolerance to CM in baked foods (tolerant or allergic/unknown).
- asthma (none, no regular inhaled corticosteroid (equivalent to BST Step 1), regular ICS (equivalent to BTS Step 2 or above).

Group allocation (active vs placebo) will be concealed throughout the study until completion of the 2nd visit of the exit DBPCFC at 12 months.

The schema for treatment allocation will be as follows:

¹³ Altman DG, Bland JM. Treatment allocation by minimisation. BMJ. 2005 Apr 9; 330(7495): 843.

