5.5 PHASE 2 - CONVENTIONAL ORAL IMMUNOTHERAPY

In phase 2, subjects will receive daily oral CM doses at home in an open, unblinded manner. Dose increases will be performed under medical supervision on the research Unit following the regime depicted in Table 6 ("conventional OIT"). Phase 2 will last 6 months (26 weeks) from the first updosing visit of Phase 2.

The protein content of supermarket-sourced commercial milk is 3.4g/100ml in UK and 3.0g/100ml in Spain. Therefore, the volume of milk to be delivered will vary slightly, by study site, in order to achieve the same dose of CM Protein across study sites (Table 6).

PHASE 2 UPDOSING PROTOCOL (CONVENTIONAL OIT)						
Step	Target CM protein (mg)	Supermarket milk (ml)	Milk preparation	Final dose (ml)		
	UK	SPAIN		UK	SPAIN	
1	0.04	0.0012	0.0013	0.125	0.15	
2	0.08	0.0024	0.0027	0.25	0.3	
3	0.2	0.0059	0.0067	0.6	0.7	
4	0.4	0.0118	0.0133	0.12	0.15	
5	1	0.0294	0.0333	0.3	0.35	
6	2.5	0.0735	0.0833	0.75	0.8	
7	6	0.175	0.2	0.2	0.2	
8	15	0.45	0.5	0.4	0.5	
9	30	0.9	1.0	0.9	1.0	
10	60	1.75	2.0	1.75	2.0	
11	135	4.0	4.5	4.0	4.5	
12	255	7.5	8.5	7.5	8.5	
13	510	15	17	15	17	
14	1020	30	34	30	34	
15	2040	60	68	60	68	
16	4080	120	136	120	136	

Table 6. Phase 2 updosing protocol (conventional OIT)

Although there are 16 steps to the OIT protocol in Phase 2, we expect at least 95% of participants to be able to commence the protocol at Step 7+ (i.e. with undiluted supermarket-sourced milk), and thus complete the full protocol within the 6 months allocated:

- Over two thirds of participants (i.e. those in groups S and O) are expected to reach 60mg CM protein by the end of phase 1, which corresponds to step 10.
- On the basis of population threshold data for cow's milk, we expect 90% of participants (even those receiving placebo in phase 1) to tolerate step 7 (6mg CM protein).

The inclusion of Steps 1-6 are to allow those few participants who remain very sensitive to low doses of CM protein to continue to participate in the study.

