5.8 OTHER ASSESSMENTS

5.8.1 ALLERGY SKIN PRICK TESTING

Skin prick testing (SPT) will be performed using ALK lancets (ALK-Abelló, Hørsholm, Denmark) on the volar side of the forearm of study participants, according to local standard operating procedures consistent with national guidelines.¹⁴

SPT will be measured at 15 minutes: the wheal will be traced around using pen and then an imprint taken with cellophane tape (e.g. sellotape); mean wheal diameter (average of longest length and its perpendicular width) will be measured.

SPT will be performed at the initial screening visit, 6 and 12 months after starting immunotherapy, using:

- Commercial extracts of whole CM and casein (ALK-Abelló, Hørsholm, Denmark), together with histamine positive and saline negative controls.
- Titrated SPT (end-point titration, EPT), to fresh* CM at the following concentrations:
 - neat, and
 - diluted (with sterile saline) at 1/10, 1/100, 1/1000, 1/10,000, 1/100,000

In addition, at *each* initial DBPCFC visit, SPT will be performed to fresh* CM and commercial CM extract (together with positive and negative control) prior to challenge. The wheal response will then be measured at approximately 30 minute intervals thereafter, until the wheal has reduced to 3mm or less, or the patient is discharged.

The time taken for the mean wheal size (elicited by SPT using neat milk or commercial extract) to reduce to 3mm (PT3) will be calculated using the following formula:

$$PT3 = T_1 + (3-W_1) \times \frac{T_2 - T_1}{W_2 - W_1}$$

where: T_1 = time when wheal diameter has reduced to < 3mm

W_1 = size of wheal at T_1 .

T_2 = time when wheal diameter has reduced to just above 3mm.

W_2 = size of wheal at T_2 .

*Fresh CM is not readily available in Spain. Therefore, SPT will be performed to freshly thawed cow's milk sourced from the UK market. Aliquots of fresh CM from the same batch of CM will be prepared in both centres and the frozen for use throughout the study for SPT. This has the added advantage of the same CM product being used throughout in both centres. We have previously demonstrated that a single freeze-thaw cycle of fresh CM does not affect SPT responses to CM.

¹⁴ http://www.bsaci.org/Guidelines/Skin_Prick_Testing.pdf

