7. STATISTICS AND DATA ANALYSIS

7.1 SAMPLE SIZE ESTIMATION

The primary objective of the study is to assess the impact of a 6 month SLIT pretreatment phase on the safety of conventional OIT in children with persistent cow's milk allergy. The primary outcome is the proportion of participants experiencing adverse events classified as mild non-transient symptoms or more severe (see table 9) during CM-OIT (phase 2), in those who have received SLIT pretreatment (group S) compared to placebo (group C). As a secondary outcome, we will assess whether any effect of SLIT is dependent on the sublingual route, by including a third treatment group who have the same dosing regimen as the SLIT group but take the dose orally, omitting the sublingual phase (group O).

The expected natural resolution rate in CM allergic children beyond preschool age is less than 10% in a 6 months period.²⁷ Up to 70% of children undergoing conventional OIT for CM allergy experience mild, transient symptoms e.g. oropharyngeal itch [20.23.38]. A previous study in 9 peanut-allergic subjects showed a 75% relative reduction in mild non-transient symptoms (or symptoms of greater severity) during OIT as a result of the SLIT pretreatment.²⁸ Assuming 10% loss-to-follow-up, we calculate that a sample size of 66 participants (allocated 1:1:1 to the treatment groups) will detect a difference in the rate of children experiencing mild, non-transient symptoms from 70% in the OIT-alone group to 18% in the group undergoing SLIT pre-treatment prior to OIT (i.e. a 75% reduction), with 80% power at a significance level of $p<0.01666$ (Bonferroni correction) to allow for three pairwise comparisons (to ensure the overall risk of type I error is under 5%).

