7.2.1 ANALYSIS OF PRIMARY ENDPOINT

The primary analysis will compare the proportion of participants experiencing adverse events classified as mild non-transient symptoms or more severe (see table 9) during CM-OIT (phase 2), in those who have received SLIT pretreatment (group S) compared to placebo (group C) using a two-sided Fisher's exact test at a $p<0.05$ level of significance.

²⁷ Wood. J Allergy Clin Immunol. 2013 March ; 131(3): 805–812

²⁸ Narisety et al. J Allergy Clin Immunol. 2015 May;135(5):1275-82.e1-6.

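### Allocation is stratified by centre but the primary S versus C test pools the two centres, which gives up some power if reaction rates differ materially between London and Madrid

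*Combined protocol and SAP*

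**What the plan says.** Allocation (section 5.3.1) uses an online minimisation tool "with a random element using a weighting probability of 0.8, stratified by centre", with six baseline variables in the minimisation.

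The primary analysis (section 7.2.1) compares the proportion with a qualifying Phase 2 adverse event "in those who have received SLIT pretreatment (group S) compared to placebo (group C) using a two-sided Fisher's exact test" at the 0.05 level. It has no centre term and no strata. Section 7.2.2 also uses Fisher's exact test for adverse-event proportions and the food-challenge outcomes, again without centre. Its one covariate model, a logistic regression for adverse events, lists age, gender, asthma status and prior anaphylaxis and leaves room for other factors. Centre is not named.

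On the Phase 2 product, section 5.5.3 says "Locally-sourced supermarket milk will be used for doses". Section 5.5 gives protein contents of 3.4 g/100 ml (UK) and 3.0 g/100 ml (Spain) and says that "the volume of milk to be delivered will vary slightly, by study site" so that both sites deliver the same protein dose.

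The sample size (section 7.1) is 66 participants, 1:1:1, with 10% loss, to detect a fall "from 70% in the OIT-alone group to 18% in the group undergoing SLIT pre-treatment" with 80% power at 0.01666.

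**The concern.** Stratifying allocation by centre aims to balance the arms within each centre. If the centres have different event rates, part of the variation in the pooled table is between centres, and the design has already removed that part from the treatment comparison. A test that ignores the strata still counts it as noise. Its true size then falls further below nominal, and it tends to have less power than a test that conditions on centre.

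Centre rates could differ here. The outcome turns on a low threshold (mild transient against mild non-transient), events are graded at the site, Phase 2 is open label, and some management decisions are left to the local investigator. These are reasons to allow for a difference. They do not show that one exists.

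What is at stake is efficiency in a comparison with about 20 participants per arm. It matters most if the true effect is smaller than planned, and the planned effect rests on a study of 9 peanut-allergic participants.

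**Working it through.** **Inputs from the documents.** 22 per group. After 10% loss, 22 × 0.9 = 19.8, taken as 20 evaluable. Event rates are 70% (C) and 18% (S); a 75% reduction is exactly 70 × 0.25 = 17.5%. The test is two-sided Fisher, at 0.05 in section 7.2.1 and 0.01666 in section 7.1.

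**Assumed.** The centre split, the control rate in each centre, and a treatment odds ratio common to both centres. S and C have equal numbers within each centre.

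**Step 1: the plan's own figure.** Exact Fisher power with 20 per arm at 0.05/3 is 78.5% for 70% v 17.5%, close to the stated 80%, and about 77% with 18% as printed. At 0.05 it is 88.4%. The mismatch between 0.01666 and 0.05 is a separate matter and affects power more than centre does.

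**Step 2: the two tests.** Let *x_k* be the events in S in centre *k*, and *m_k* the total events in S and C there.

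- Pooled Fisher: given *m_1 + m_2*, the sum *x_1 + x_2* is hypergeometric.
- Stratified exact test: given *m_1* and *m_2* separately, *x_1 + x_2* follows the convolution of two hypergeometric distributions.

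Both p-values sum the probabilities of all outcomes no more likely than the one observed. Power is the sum of the binomial probabilities of every outcome with p < 0.05.

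**Step 3: rates by centre.** logit(S rate in centre *k*) = logit(C rate in centre *k*) + θ, with θ chosen so that the average S rate is 18% or 35%. Example: control 80/60% has odds 4 and 1.5. An odds ratio of 0.083 gives S odds of 0.332 and 0.1245, so S rates of 24.9% and 11.1%, which average 18%.

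**Step 4: power (%), pooled v stratified, two-sided 0.05.** Gains are computed before rounding.

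| Control rates | S 18%, 10+10 per arm | Gain | S 35%, 10+10 per arm | Gain | Gain, S 18%, 11+11 per arm |
|---|---|---|---|---|---|
| 70/70 | 88.4 v 88.1 | -0.3 | 46.8 v 46.8 | 0.0 | +0.1 |
| 75/65 | 88.5 v 88.7 | +0.2 | 46.7 v 47.8 | +1.1 | +0.2 |
| 80/60 | 88.8 v 90.2 | +1.4 | 46.4 v 50.6 | +4.1 | +0.6 |
| 85/55 | 89.4 v 92.3 | +3.0 | 46.0 v 54.6 | +8.7 | +1.6 |
| 90/50 | 90.1 v 94.5 | +4.5 | 45.2 v 60.1 | +14.9 | +2.9 |

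With 11+11 and S 35% the gain runs from less than 0.2 to 12.2 points.

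**Step 5: where stratifying loses (S 18%).** With a 13/7 split and control rates 65/75%, pooled 86.5 v stratified 86.3. With 15/5 and identical centres, 88.42 v 87.96, a loss of 0.47 on unrounded figures. With 17/3 and 65/75%, 83.39 v 82.86, a loss of 0.53.

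**Step 6: type I error.** With no effect and rates of 90/50% in both arms, true size is 1.3% pooled and 1.8% stratified, both below 5%.

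**Step 7: precision within a centre.** With 10 per arm at 70% v 18%, the 95% half-width is 1.96 × √(0.7×0.3/10 + 0.18×0.82/10) = 1.96 × √0.03576 ≈ 0.37, or ±37 points.

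**The case against.** The strongest reply is that this is a small, optional gain. No validity problem exists: pooled Fisher keeps its error rate below nominal. At the plan's own 70% v 18%, pooled power with equal-sized centres does not fall as the centres diverge; it rises from 88.4% to 90.1%, and the stratified test simply rises faster. Gains of 3 points or more at that effect need control rates about 30 points apart. If all 22 per arm are analysed, as the intention-to-treat rule in section 7.2 may allow, the gains shrink further, so part of the advantage comes from the coarseness of tables with 10 per stratum. Centre could also enter the logistic regression in 7.2.2. All of this stands, and it limits the point to efficiency. It does not remove the larger gains at a smaller effect, and a secondary model that does not name centre does not change the primary test.

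Four stronger readings are tempting, and the documents do not support them.

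- *Pooling loses power whenever centre rates differ.* It does not. Step 5 has cases where rates differ and pooled Fisher is slightly better.
- *Local milk means different reaction rates.* Section 5.5 varies volume so that protein dose matches. At step 15, 60 ml × 34 mg/ml and 68 ml × 30 mg/ml both give 2040 mg. The remark in section 5.8.1 that "Fresh CM is not readily available in Spain" concerns skin-test material.
- *Results by centre would show whether the effect holds with each centre's milk.* At ±37 points they cannot, and product is confounded with population and local practice.
- *Stratifying is free.* It can cost about half a point.

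**Conclusion.** The analysis does not use the factor by which allocation is stratified. The pooled test is valid and conservative. Compared with the like-for-like exact test stratified by centre, with 10+10 per arm, it gives up about 1 to 5 points of power at the planned effect when control rates are 20 to 40 points apart, and about 4 to 15 points if the S rate is 35%. With 11+11 per arm the gains from stratifying are smaller: about 0.1 to 2.9 points at S 18%, and up to 12.2 at S 35%. For small centre differences the two tests are practically equal and pooled Fisher may be marginally ahead.

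These figures rest on assumed centre rates, an assumed even split, equal arms within centres and a common odds ratio. The documents supply none of these. The point is a modest gain in efficiency, worth taking because it costs so little. It casts no doubt on the validity of the primary result.

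**What to change.** In section 7.2.1, name as the primary test the two-sided exact conditional test of S versus C stratified by centre (exact Cochran-Mantel-Haenszel over the two 2×2 tables), and report the Mantel-Haenszel risk difference with its 95% CI. Use the same form for S versus O and the other yes/no outcomes in section 7.2.2. Keep pooled Fisher as a sensitivity analysis. If S minus C differences by centre are shown, label them descriptive.

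Set this down before unblinding, since a choice to stratify made after seeing centre rates would not be credible.

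The cost is a change of wording and a standard exact routine, with no extra participants, visits or data. The statistical cost is about half a point of power if the centres are identical or differ little, especially with an uneven split.

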5.5.4 CHANGES TO THE PROTOCOL DUE TO REACTIONS

The same criteria and measures described in 5.3.2.4 for phase 1 will be followed in phase 2.

5.5.5 CONCOMITANT MEDICATION DURING PHASE 1 & 2

Participants may continue usual medications, including those taken for asthma, rhinitis, and eczema during the study. Antihistamines must be stopped prior to screening and DBPCFC visits as per section 5.2.1. Participants (or their parents) will be asked to document any use of medication (including rescue medication) in home diary cards.

5.5.5.1 MANAGEMENT OF RECURRENT SYMPTOMS

While treatments for recurrent AEs are permitted (e.g. H1-antihistamines), these medicines should not be routinely used in advance of symptoms due to OIT. Antihistamines may be taken after review by the local chief investigator for short-term symptomatic relief only, unless required for the treatment of allergic rhinitis during the study. If started, the use of these medications should be minimized, and then discontinued at the earliest opportunity.

Symptomatic treatment not involving antihistamine for chronic/recurrent AEs is permitted (subject to compliance with the exclusion criteria for the study), but should be used only where dose reduction has not on its own been effective. Any medicine instituted for treatment of symptoms (AEs) related to OIT doses must be withdrawn by 4 weeks prior to the exit DBPCFC at 12 months.

5.6 12 MONTH ASSESSMENT / EXIT DBPCFC

All subjects will be offered a DBPCFC to CM and receive further dietary advice.

5.6.1 DBPCFC

All subjects will be invited to undergo a further DBPCFC to CM at approximately 12 months as described in 5.2. Both DBPCFC visits should take place between 24-30 weeks after commencing Phase 2 OIT. No OIT dose should be administered on the same day as a challenge visit. The purpose of this challenge is to determine the effect of the treatment in participants' threshold of reactivity. Successful desensitization will be defined as a negative outcome to a cumulative dose of 8g CM protein.

5.6.2 DIETARY ADVICE

Future advice will be provided following the second visit at the 12 months DBPCFC regarding CM consumption, based on the threshold of reactivity at DBPCFC as follows:

- Participants reacting at doses below 1.4g CM protein cumulative will be assessed by the study investigators and provided with advice relating to CM exposure according to local clinical protocol. Many of these participants may be able to tolerate small amounts of CM in baked foods: where appropriate, this will be assessed as part of the participant's routine clinical care.
- Participants able to tolerate at least 1.4g CM protein will be asked to continue their daily CM exposure at the same dose taken immediately prior to the 12 month DBPCFC. This regular CM intake will ensure that the effect of the treatment is maintained. Participants (and their families) will also be given appropriate advice allowing them to include CM-containing products up to the amount they tolerate at the 12 month DBPCFC.

All subjects will also undergo repeat skin prick testing and HRQL assessments at 12 months.

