5.2.3 EXIT DBPCFC AT 12 MONTHS

The challenge will consist of up to nine consecutive, increasing doses of CM (or placebo) at 20-30 minute intervals, up to a cumulative dose of 8 gram CM protein, as shown in table 3.

Exit DBPCFC to Cow's Milk		
Dose	CM protein (mg)	Approx. volume of CM (ml)
1	0.5	0.015
2	3	0.09
3	10	0.3
4	30	0.9
5	100	3
6	300	9
7	1000	30
8	3000	90
9	3600	105
Cumulative dose	8044	250
2 hours observation period following last dose to monitor for signs of reaction		

Table 3. Dosing protocol for exit DBPCFC to CM.

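### The exit dietary rule (section 5.6.2) uses two different quantities: a reaction at 1000 mg fits neither branch, and a reaction at 3000 mg can leave a daily dose above the amount tolerated

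*Combined protocol and SAP*

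**What the plan says.** Section 5.6.2 of the protocol states that advice after the second exit challenge visit rests on the threshold of reactivity found at that challenge. It then gives two branches.

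- Lower branch: "Participants reacting at doses below 1.4g CM protein cumulative will be assessed by the study investigators" and advised under local clinical protocol.
- Upper branch: children who tolerate 1.4 g or more are "asked to continue their daily CM exposure at the same dose taken immediately prior to the 12 month DBPCFC". The stated reason is to maintain the treatment effect. The same bullet adds that families will be advised how to "include CM-containing products up to the amount they tolerate at the 12 month DBPCFC".

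The exit challenge (section 5.2.3, Table 3) has "up to nine consecutive, increasing doses of CM (or placebo) at 20-30 minute intervals, up to a cumulative dose of 8 gram CM protein". The daily doses come from Table 6 in section 5.5, which ends at step 15 (2040 mg) and step 16 (4080 mg). Under section 5.5.2, a child who reaches step 16 stays on it until the one-year assessment is complete.

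**The concern.** The lower branch asks at what cumulative dose the child reacted. The upper branch asks how much the child tolerated. In a stepped challenge these differ by the size of the step that caused the reaction, so a single 1.4 g cut-point applied to both need not place every child. The step that straddles 1.4 g is the one at risk.

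The upper branch also carries two instructions with different reference points. The daily dose is fixed by what was taken before the challenge, whereas other milk products are fixed by what was tolerated at it. For a child whose daily dose is larger than the amount tolerated at challenge, these do not agree, and the first does not follow from the basis that the section gives for its advice.

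What is at stake is the instruction on home milk exposure given to children who have just reacted under observation. A secondary matter is exposure in the three months before the 15-month quality-of-life assessment (section 5.7).

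**Working it through.** **Inputs.** Exit challenge doses (Table 3): 0.5, 3, 10, 30, 100, 300, 1000, 3000 and 3600 mg. Cut-point (section 5.6.2): 1400 mg. Top daily doses (Table 6): 1020, 2040 and 4080 mg at steps 14, 15 and 16.

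**The plan's own figure.** The nine doses sum to 8043.5 mg, which rounds to the 8044 mg printed in Table 3.

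**Testing each outcome.** For a first reaction at dose k, the cumulative dose at reaction is the sum of doses 1 to k, and the amount tolerated is the sum of doses 1 to k−1. The lower branch needs the first to be under 1400 mg. The upper branch needs the second to be 1400 mg or more.

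| First reaction at | Cumulative at reaction (mg) | Tolerated (mg) | Lower branch | Upper branch |
|---|---|---|---|---|
| Doses 1–6 | 0.5 to 443.5 | 0 to 143.5 | yes | no |
| Dose 7 (1000 mg) | 1443.5 | 443.5 | no | no |
| Dose 8 (3000 mg) | 4443.5 | 1443.5 | no | yes |
| Dose 9 (3600 mg) | 8043.5 | 4443.5 | no | yes |
| None | – | 8043.5 | no | yes |

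The dose 7 row fits neither branch.

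**Other readings of the cut-point.**

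- If 1.4 g is a rounding of the 1.44 g in inclusion criterion 3 (section 4.1), 1443.5 mg is still not below 1440 mg, and the gap stays.
- If both branches are read as single doses, dose 7 moves to the lower branch (1000 is below 1400). Dose 8 then fits neither: the child reacts at 3000 mg, and the largest single dose tolerated is 1000 mg.
- The gap closes if the lower branch is read as a single dose and the upper as cumulative. But the lower branch is the one that prints the word cumulative.

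Inclusion criterion 3 meets the same boundary without a gap, because it counts a reaction at 1.44 g or less as allergic.

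**Daily dose against amount tolerated, dose 8 reactors.**

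- Step 14: 1020 / 1443.5 = 0.71, so no conflict.
- Step 15: 2040 / 1443.5 = 1.41.
- Step 16: 4080 / 1443.5 = 2.83.

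Both upper steps lie below the 4443.5 mg cumulative dose at reaction. For dose 9 reactors the tolerated 4443.5 mg exceeds 4080 mg, so the conflict is confined to dose 8.

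**Can step 16 be reached?** At the minimum of 10 days per step, a child starting Phase 2 at step 11 needs (16 − 11) × 10 = 50 days. From step 9 it is 70 days and from step 1 it is 150 days. Phase 2 lasts 26 × 7 = 182 days, so the combination is possible within the schedule.

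**The case against.** **The gap is a wording slip with an obvious intent.** Section 3.1.2 uses 1.4 g to define partial desensitisation, and a dose 7 reactor fails that definition. On the printed wording such a child is not told to continue, having tolerated only 443.5 mg. Individual assessment looks like the intended route. This stands as a reading of intent, and it limits the consequence of the gap. It does not supply the missing assignment, since no other section gives one.

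**The two clauses govern different things.** One maintains an established dose, first given under supervision and then taken at home for at least 10 days (section 5.5.2). The other concerns foods added to it. The protocol may mean the established dose to override the challenge result, which is a coherent position. But the section says the advice rests on the challenge threshold, and it does not address the case where the two disagree. Section 8.2 lets the clinician depart from the protocol in the child's interest. That allows a remedy in an individual case but does not reconcile the text.

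**Stronger inferences that the documents do not support.**

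- A reader might infer that the rule orders some children to stop milk. It does not: the lower branch refers them to investigator assessment and local protocol.
- A reader might infer that the continued dose exceeds the child's threshold. A dose 8 reaction places the cumulative threshold between 1443.5 and 4443.5 mg, and both 2040 and 4080 mg lie inside that interval. It is true that 4080 mg exceeds the 3000 mg single step, but that compares a daily dose with the last increment of a cumulative series.
- A reader might infer that the two sites will give opposite instructions. The text tells neither site to continue a dose 7 reactor, and tells both the same thing about a dose 8 reactor.

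**Conclusion.** The point holds as a drafting defect in section 5.6.2 with two parts. First, one of the nine possible reaction steps, dose 7, is assigned to no branch. Second, children who react at dose 8 while taking step 15 or 16 are told to continue a daily dose 1.4 or 2.8 times the amount shown to be tolerated, while other milk products are limited to that amount.

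This rests on reading the upper branch's 1.4 g as cumulative. The lower branch says so explicitly, and section 5.6.1 also defines success by a cumulative dose. The single-dose reading moves the gap to dose 8 and does not remove it.

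The number of children affected cannot be derived. The documents give no expected distribution of exit reaction steps, nor of daily doses at exit.

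The reach is limited. The advice follows the exit challenge, so it cannot alter the Phase 2 primary outcome or the 6- and 12-month outcomes. At most it could affect the 15-month quality-of-life time point, and allocation stratified by centre (section 5.3.1) limits any between-arm effect of differing site practice. The main reason to correct it is clarity about home exposure after a reaction.

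**What to change.** In section 5.6.2, define both branches on the same quantity, either cumulative dose tolerated or cumulative dose at reaction, so that each possible Table 3 outcome, including no reaction, falls in exactly one branch. Check the result against inclusion criterion 3 and the partial-desensitisation definition in section 3.1.2, which use nearly the same cut-point.

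For children whose daily dose exceeds the amount tolerated at the exit challenge, reconcile three statements: that advice rests on the challenge threshold, that the daily dose continues unchanged, and that other products are limited to the amount tolerated. The investigators should settle which clinical rule applies; this review proposes none.

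The cost is a few words in one section. No procedure, visit or sample-size change follows.
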